2.1 Primary objective

To assess the feasibility of deploying the iLet bionic pancreas system in the insulin-only configuration to

pump-naïve MDI users with type 1 diabetes, in the setting of being recruited from community-based primary care practices and being trained and managed by primary care providers (PC group), and in pump- and CGM-experienced (sensor-augmented pump or hybrid closed-loop) users with type 1 diabetes recruited from, trained, and managed by an academic endocrinology practice (EN group). In both practice settings, the exclusive use of telehealth (TH) visits will be assessed, as will use of in-person (IP) visits.

We will enroll 40 adult volunteers (18-85 years old) with type 1 diabetes, 20 who are insulin pump naïve MDI users enrolled from community primary care practices by University of Colorado Family Medicine (PC group) and 20 who are technology-savvy sensor-augmented pump or hybrid closed-loop users enrolled by the Massachusetts General Hospital Diabetes Clinical Research Center (EN group). Ten of the participants at each center will be trained and managed throughout the trial using in-person visits (PC-IP and EN-IP groups) and the other ten from each center will be trained and managed throughout the trial exclusively via telehealth visits (PC-TH and EN-TH groups). The 40 participants will be evenly divided into these four groups, but not by randomization. Participants will be assigned to either the in-person or telehealth arm based on the participant's preference, the participant's location, and the discretion of the investigator. Subjects in all four groups will each participate, in random order, in one 14-day study arm under their own usual care (UC arm) and one 14-day study arm under the insulin-only configuration of the iLet bionic pancreas (iLet arm).

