2.2 Secondary objectives

1. To obtain preliminary data on the quality of glycemic control among the PC and EN groups, with separate analyses in the IP and TH sub-groups, and in the UC and iLet arms within those groups, which will be used to power a larger study with a glycemic control metric as the primary outcome. Our hypotheses are that glycemic control, with key outcomes being group mean CGM glucose, the group mean time with CGM glucose less than 54 mg/dl, and the group mean time with CGM glucose in the 70–180 mg/dl range, will be similar in the PC-IP group and the EN-IP group, and in the PC-TH group and the EN-TH group in the iLet arm. Additionally, we hypothesize that glycemic control will be similar in the PC-TH group and the PC-IP group, and in the EN-TH group and the EN-IP group in the iLet arm. Further, we hypothesize that there will be a larger difference in glycemic control metrics between the UC arms versus the iLet arm in the PC group than there will be in the EN group.
2. To assess the impact of the insulin-only configuration of the iLet bionic pancreas system on psychosocial outcomes (including quality of life, fear of hypoglycemia, and diabetes distress) among study participants. Secondary analyses will be conducted between the telehealth and in-

person arm, the EN and PC groups, and the iLet and UC arms.

3 Participant Selection

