5.6 Study Visit Procedures

5.6.1 Visit Procedures for in-person (IP) visits

5.6.1.1 Day 1 Visit (Visit 2):

- The body weight of the participant will be documented.
- A urine pregnancy test will be performed in participants of child-bearing potential at the start of the first arm. If the test is positive, the participant will be informed of the result and the visit will be ended. The date of the last menstrual period will also be documented.
- Study staff will review any changes in the participant's medical history or medications to ensure continued eligibility, and any adverse events that may have occurred since their screening visit.

5.6.1.1.1 Participants randomized to usual care:

- Study staff will provide supplies and review the study procedures.
- Participants will be trained how to insert, maintain and use the Dexcom G6 (in blinded mode if they are not a CGM user).
- The participants will wear a Dexcom G6 sensor and study staff will confirm they are doing it properly.

5.6.1.1.2 Participants randomized to bionic pancreas:

- Study staff will provide supplies and review the study procedures.
- Participants will be trained how to insert, maintain and use the Dexcom G6 CGM.
- The participants will wear a Dexcom G6 sensor and study staff will confirm they are doing it

properly.

- Participants will be trained to use the iLet, including navigating the GUI, filling and installing cartridges and inserting infusion sets.
- Participants will set up the iLet and insert the infusion set and study staff will confirm they are doing it properly.
- The control algorithm will be initialized with the participant's weight.
- If using an insulin pump (EN group), their own insulin infusion pump will be stopped and disconnected if applicable, and its infusion set will be removed
- If using MDI therapy (PC group), they will be instructed not to take any additional insulin injections once the bionic pancreas is started, unless instructed to do so by study staff
 - Participants on multiple daily injections (MDI) may be started on the iLet without a need for adjustment of their long-acting insulin dose. The new equilibrium will not be reached until all the long-acting insulin has completely cleared their system, which may take 48 hours or more. Participants must be advised that they may see escalating dosing by the iLet during this period.

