- If using MDI therapy (PC group), they will be instructed not to take any basal insulin starting the morning of this study visit, and no additional insulin injections once the bionic pancreas is started, unless instructed to do so by study staff
 - Participants on multiple daily injections (MDI) may be started on the iLet without a need for adjustment of their long-acting insulin dose. The new equilibrium will not be reached until all the long-acting insulin has completely cleared their system, which may take 48 hours or more. Participants must be advised that they may see escalating dosing by the iLet during this period.
 - Investigators may consider starting MDI users at the "higher" glucose target setting. If the "higher" setting is used, wait ~2 days before moving down to the default target.
- Participants will complete Clarke's Instrument for Impaired Awareness of Hypoglycemia.
 - Participants with a score > 4 will be instructed to check BG at 2am for the first 2 nights using the iLet

5.6.2.2 Mid-period Follow Ups (Visits 3, 4, 6, and 7):

- Participants may complete a virtually supervised site change, as needed or requested based on participant's prior experience and comfort level.
- All participants will have a virtual phone visit on Day 2 and Day 5 (+/- 2 days) to assess device adaptation, glucose control, and to answer any questions the participant may have.
- Study staff will query the participant for any adverse events and assess the participant's ability to follow protocol and, if applicable, use the device at this time.

5.6.2.2.1 *BP arm:*

- Participants on the BP will be asked about their glucose control and study staff will educate as needed. The study staff may suggest a change to the permanent glucose target if indicated.

5.6.2.2.2 *UC arm*

- No modifications will be made to dosing regimens for participants in the usual care arm.
- Study staff will confirm the participant is wearing the study CGM, and answer any questions the participant may have about the study CGM. They will remind the participant to replace the study CGM after 10 days.

5.6.2.3 Crossover Visits (Visit 5):

- At the end of the first study period (Day 14 [+2]), participants will have a virtual study visit and answer the post questionnaires for the study arm.
- Study staff will review any changes in the participant's medical history or medications to ensure continued eligibility, and any adverse events that may have occurred since their screening visit.

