6.2 Primary endpoint

- Percentage of individuals with mean CGM glucose <183 mg/dL (corresponding to an estimated HbA1c of <8.0%) on days 3-14, by group.

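### Participant instructions need reconciling: the response to the high-glucose alarm, basal insulin at iLet start by visit mode, and (minor) the sensor-offline time

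*Combined protocol and SAP*

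**What the plan says.** **High-glucose alarm.** Section 5.7.3 describes an optional iLet alarm for CGM glucose above 300 mg/dl for 90 minutes. The bullet under it trains participants to check with the study meter and then treat hypoglycemia, with a reference to section 5.7.2. The bullet under the low-glucose alarm says the same. For confirmed hyperglycemia, section 5.7.2 has participants inspect the infusion set, reservoir and device, and check blood ketones if the reading stays above 300 mg/dl for more than 90 minutes. It also has them call the study team if such a reading is unexplained.

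**Basal insulin when an MDI user starts the iLet (PC group).** The telehealth text, at Day 1 (5.6.2.1.2) and at crossover (5.6.2.3), says "they will be instructed not to take any basal insulin starting the morning of this study visit" and then "no additional insulin injections once the bionic pancreas is started, unless instructed to do so by study staff". The in-person text, at Day 1 (5.6.1.1.2) and at crossover (5.6.1.3), tells participants only "not to take any additional insulin injections once the bionic pancreas is started, unless instructed to do so by study staff". Both Day 1 sections add that MDI users "may be started on the iLet without a need for adjustment of their long-acting insulin dose", and that a new equilibrium must await clearance of that insulin, "which may take 48 hours or more".

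**Where this meets the analysis.** Section 2.2 states "we hypothesize that glycemic control will be similar in the PC-TH group and the PC-IP group". Section 2.1 states "The 40 participants will be evenly divided into these four groups, but not by randomization". The primary endpoint is assessed "on days 3-14, by group" (section 6.2).

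**Sensor offline.** Section 5.7.2 says in one bullet that a sensor offline for more than 4 hours alerts as failed and should be replaced. In a later bullet the participant starts a new sensor after more than 3 hours.

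**The concern.** These are insulin and alarm instructions for adults who, in the PC group, have never used a pump and are managed in a care model that the protocol calls previously untested (section 8). Staff will train from this text. Where two sections give different actions for the same reading, or one visit mode has a rule that the other lacks, what a participant is taught depends on which page the trainer reads.

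The basal item also touches the design. PC-TH versus PC-IP is a stated comparison between groups formed by preference, location and investigator discretion. If the two modes start the iLet under different insulin instructions, that difference becomes part of what visit mode means, and the protocol neither acknowledges nor explains it.

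**Working it through.** The plan states no figure on this point, so the check is mainly a side-by-side reading.

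| Item | One place | Other place | Relation |
|---|---|---|---|
| Alarm above 300 mg/dl for 90 min | 5.7.3: measures for hypoglycemia | 5.7.2: check set, reservoir and device, then ketones; call if unexplained | Contradiction |
| Basal dose on the morning of iLet start, MDI users | 5.6.2.1.2 and 5.6.2.3 (telehealth): held | 5.6.1.1.2 and 5.6.1.3 (in person): not addressed | Unexplained difference |
| Sensor offline | 5.7.2: more than 4 h | 5.7.2, later bullet: more than 3 h | Two times for one action |

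**Alarm.** The high-alarm bullet repeats the low-alarm bullet, so it is probably a copied line. Section 5.7.3 also speaks of both BP arms, although this trial has one iLet arm, which likewise suggests carried-over text. In section 5.7.2, carbohydrate treatment depends on the meter confirming a low, which limits the harm from a literal reading.

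**Basal insulin.** The difference appears at both Day 1 and crossover, so it is not a single slip. The pump instruction for the EN group is the same in both modes. The sub-bullet on long-acting insulin may mean only that no taper is needed, but directly under the telehealth hold its meaning is unclear.

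**Reach.** The basal item concerns 10 PC-TH + 10 PC-IP = 20 of 40 participants. How many would actually differ is unknown. Anyone whose only basal dose falls in the evening, after the start, is treated alike by both texts. The alarm item reaches all 40 in the iLet arm if the optional alarm is switched on. The sensor item reaches all 40.

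**Could the basal difference matter on days 3-14?** The documents allow only a bound on time.

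- The window is 12 days × 24 h = 288 h.
- For a once-daily morning dose, omitting the visit-day dose moves the last injection 24 h earlier. Clearance then ends at most 24 h earlier: 24/288 = 8.3% of the window.
- Assume clearance in exactly 48 h, a dose between 07:00 and 12:00, and day 3 starting at midnight. With the dose taken, 7 to 12 h fall in the window (7/288 = 2.4%; 12/288 = 4.2%). With it omitted, 0 h do.
- If day 3 is counted from 48 h after the iLet start, it is 0 h either way.

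Turning hours into glucose needs an assumption. If glucose were shifted by 50 mg/dl throughout those hours (illustrative, not from the documents), a participant's mean would move by 50 × 7/288 = 1.2 to 50 × 12/288 = 2.1 mg/dl, or 50 × 24/288 = 4.2 mg/dl at the outer bound. The result scales in proportion to the assumed shift. For comparison, the Bridging Study (section 12.1.8) reports 155 ± 13 mg/dl on the iLet with lispro or aspart. To cover the 183 − 155 = 28 mg/dl from that mean to the primary threshold within 12 h, the shift would have to be 28 × 288/12 = 672 mg/dl.

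**The case against.** The strongest reply is that little here is a true conflict.

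- **Basal insulin.** Silence is not contradiction. In-person staff can settle the morning dose individually, both texts let study staff instruct otherwise, and the difference may be deliberate. This stands: a reader might infer that the two modes give opposite orders, and the documents do not say that. What remains is a difference by mode with no reason given.
- **Alarm.** The bullet refers to section 5.7.2, which contains the hyperglycemia steps, and section 5.7.3 is titled for both conditions. A reader might infer that participants are told to take carbohydrate at 300 mg/dl. Section 5.7.2 does not support that, because carbohydrate follows only a meter-confirmed low. The wording is still contradictory as written.
- **Sensor.** A reader might infer that the two times cannot both be obeyed. They can: a participant who replaces the sensor at 3 hours never reaches the 4-hour alert. Both times also lie inside the separate 6-hour limit without CGM input, with glucose self-checks at least every two hours while the sensor is offline.
- **Safeguards.** These include Day 2 contact, an optional higher starting target, 2 am checks on the first two nights for Clarke scores above 4, the low-glucose alarms, a provider on call at all times and the stopping rule in section 9.2. They limit harm, but they do not tell a trainer which sentence to teach.
- **Inference.** The trial is a feasibility study without a power calculation (section 6.6), and its p-values are not for inference (section 6.7). This stands, so the case for change rests on clear instructions and a clean description of the groups rather than on error rates.

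**Conclusion.** The point holds in a limited form. The high-alarm response contradicts section 5.7.2. The basal instruction differs by visit mode without a stated reason, for a group of 20. The two sensor times are a minor inconsistency of one hour. All three should be corrected, because they are safety instructions and the correction is cheap.

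A reader might go further and infer that residual long-acting insulin distorts the days 3-14 results or the iLet versus usual-care difference in the PC group. The documents do not support this. The protocol says that clearance may take 48 hours or more in both modes, so some residual insulin could be present under either text, and reconciling them would not remove it. The iLet adapts its basal delivery (section 1.2.2). The Bridging Study, shown over days 3-7 and including 12 MDI users, reports equal performance in MDI and pump users. That is supportive but not decisive, since its basal instruction is not described. The effect on days 3-14 cannot be derived. The illustrative 1.2 to 4.2 mg/dl depends on the assumed 50 mg/dl shift and the clearance timing, and supports only the judgment that it is probably small. A participant already close to 183 mg/dl could still change category.

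**What to change.** The clinical leads should reconcile:

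1. the response to the alarm above 300 mg/dl in section 5.7.3 with the hyperglycemia steps and call criteria in section 5.7.2;
2. the in-person basal text (5.6.1.1.2, 5.6.1.3) with the telehealth text (5.6.2.1.2, 5.6.2.3), including the meaning of the shared sub-bullet on long-acting insulin;
3. the two sensor-offline times in section 5.7.2.

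The training material should be aligned with the result. If the basal instruction is meant to differ by visit mode, the protocol should say so, give the reason, and have it reported as a known difference between PC-TH and PC-IP. Which instruction or time is right is for the clinical leads; no position is taken here.

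The cost is protocol wording and matching training material. No visits, participants or data items are added.

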5.7 General Study Policies for all Study Arms

- Participants will be advised not to use alcohol or other drugs in sufficient quantity to reduce sensitivity to symptoms of hypoglycemia or hinder appropriate decision-making.
- Any medical advice needed by the participants during their participation that is not directly related to the study protocol should be obtained in the usual manner with their own physician. If the participant experiences urgent or emergent medical concerns outside the scope of diabetes care and their primary care physicians, they should visit a walk-in clinic or emergency room, or if necessary, call 911.
- There are no restrictions of any kind on diet, exercise, or other activities.
- Participants will be asked to complete a daily survey in all study arms including questions about hypoglycemia and carbohydrate interventions and diabetes tasks that occurred in the prior 24 hours. Participants on the BP arm will also be asked about time disconnected from the iLet.
- Study participants will be instructed to keep fast-acting carbohydrates and a glucagon emergency kit (supplied by the study) easily accessible in case they are needed.
- Participants will be instructed to keep fast-acting insulin with them in case of a hyperglycemic emergency.
- Participants will be instructed to carry an extra sensor with them at all times. They will be taught to replace the sensor if it falls out, or after 10 days.

5.7.1 Policies for the Usual Care Arm

- Participants may be contacted between visits if needed, per the discretion of either the participant, a healthcare provider, or a member of the study team.
- The UC arm will continue its pre-study diabetes management, including approach to insulin delivery and management. Diabetes management will be handled by the participant's usual diabetes health care provider. *No adjustments to the diabetes care plan will be made by the study team.*

- Participants in the endocrinology (EN) cohort using FDA-approved devices as part of their pre-study usual care, such as a CGM system, insulin pump, or closed-loop system can continue use of their personal devices during the study period. Use of devices that are not FDA-approved is prohibited.

5.7.2 *Policies for the Bionic Pancreas Arms*

- Participants may be contacted between visits if needed, per the discretion of either the participant, a healthcare provider, or a member of the study team.
- Participants using the iLet will not be allowed to travel outside the United States or its territories for the entire time the system is in use.
- Participants may perform calibrations of the Dexcom G6 CGM if it is inaccurate relative to a BG measurement, per the device manufacturer's instructions.
- The iLet will have CGM glucose alarm settings available to the participants. Study staff will work with participants to configure the alarm settings in a way that will be most appropriate for each individual.
 - Study staff will recommend a low CGM glucose alarm be set for 75 mg/dl and a high CGM glucose alarm be set for > 300 mg/dl for 90 minutes.
- If participants receive a high or low CGM glucose alarm, they will be trained to verify the CGM glucose with a fingerstick glucose value using the Contour Next One glucometer.
 - The participant will be trained to treat hypoglycemia with rapid acting carbohydrates, in case the glucometer confirms hypoglycemia. This may be done according to their usual practice or with less carbohydrate than their usual practice since the BP system will typically have suspended insulin delivery prior to the occurrence of hypoglycemia. They will be trained to continue to monitor their glucose levels until they return to normoglycemia.
 - Participants will be trained to assess their infusion set and tubing for patency, the insulin reservoir for sufficient insulin supply, the iLet for sufficient battery power, proper functioning, and insulin delivery, in case the glucometer confirms hyperglycemia. In case hyperglycemia > 300 mg/dl persists for more than 90 minutes, they will be trained to check their blood ketone level using the Precision Xtra blood ketone meter.
 - In case ketones are ≥ 0.6 mmol/l, they will be trained to replace their infusion set and to inform study staff. They will be trained to continue to monitor their glucose and blood ketone levels until they return to normoglycemia and ketones are < 0.6 mmol/l.
 - If ketones are < 0.6 mmol/l, they will be advised to continue to monitor their glucose until it returns to normoglycemia and to repeat the ketone measurement in 90 minutes if necessary
 - If the glucometer reading is not consistent with the CGM glucose reading, participants will be trained to look for possible scenarios that could lead to an inaccurate CGM reading.
 - They will be educated about the lag between interstitial and capillary glucose readings, and to delay a calibration in times of rapid changes in glucose. They will also be trained about the standard difference between CGM and capillary glucose readings, and to consider the CGM inaccurate if it is $> 20\%$ different than their glucometer reading. If their CGM glucose is not changing rapidly and is $> 20\%$ different from their capillary glucose reading, they will be instructed to calibrate

their CGM if possible.

- A compression artifact at the site of the sensor may cause false hypoglycemic readings. This should resolve by removing the compression of the sensor.
- If there is a technical fault with the iLet, the participant will be instructed to call the clinical site immediately.
 - All contacts from a study participant will be documented. The site will be responsible for all reporting of device issues and adverse events.
 - If necessary, a staff member will meet the participant to assist with troubleshooting. This meeting may be delayed until morning if the problem occurs overnight —in this case, the participant will use their own pump or use injectable insulin until a meeting is possible. A member of the study staff (within their scope of practice and under the supervision of the site principal investigator) may advise them on how to manage their diabetes in the interim. If necessary, the iLet device may be replaced. This may require shipping a new device to the participant. For participants in the telehealth arm, a new device will either be sent via express delivery or driven to the participant if feasible. Participants will be instructed to revert to usual care until they get the iLet.
- If there is a complete failure of the iLet operation and it is anticipated that restarting it will take more than an hour, or there is physical disconnection from the iLet that lasts longer than one hour, participants may revert to usual care using their own insulin pump or with insulin injections until the iLet can be brought back online with the help of study staff. In addition, frequent BG checks (every 2 hours and before meals) will be advised for any participant not receiving CGM data in this circumstance. Every effort should be made to correct the problem as soon as possible, which should almost always be within 24 hours
- Participants will be instructed to call the study team immediately, at any time of day or night, under any of the following circumstances:
 - They have questions or concerns
 - They want assistance troubleshooting the device
 - They have unexplained glucose over 300 mg/dL for greater than 90 minutes
 - They have ketones greater than 2.5 mmol/L (Large)
 - They have ketones greater than 0.6 mmol/L for more than 90 minutes
- If the sensor fails, it should be replaced. If the sensor is offline, participants will be instructed to self-check blood glucose at least every two hours and before meals.
 - If the sensor is offline for more than 4 hours, the sensor alerts as failed and should be replaced.
 - When the CGM is offline, the iLet will continue giving basal doses based on the latest basal dosing that it had learned, allow the user to make meal announcements in exactly the same way as when the CGM was online, and automatically respond to user-entered BG values by issuing a correction dose of insulin when applicable. If the CGM sensor is not reading glucose levels, the system will provide basal insulin based on past requirements and will allow announcement of meals and entry of fingerstick BG measurements, which will be treated as CGM data and may result in administration of insulin or temporary suspension of basal insulin. The system will alarm and request a BG measurement every 2 hours when the CGM signal is not available. Participants will be trained in various ways to bring their study CGM sensor back online. This may involve replacement of the Dexcom G6 CGM sensor. If instructed by the iLet to do so, the

participant will start a new CGM sensor. If the sensor is offline for more than 3 hours, the participant will start a new sensor. The closed loop system may be used without CGM input for a maximum of 6 hours. Normal (online) BP control will resume automatically when the CGM sensor is reporting glucose values again.

- Study staff will contact Beta Bionics for additional troubleshooting as necessary.
- Participants will be instructed to announce up to three major meals a day to the iLet. The meal announcement will consist of choosing the size of the meal relative to usual meals for that participant at that time of day (Usual for me, Less, More). Participants will be trained not to announce snacks that occur between major meals.
- Participants will be trained on the interface to change the glucose targets. They will be asked to consult with study staff before making any changes to the permanent target or to setting a daily/night recurring target alteration schedule.
- Participants will be asked to change their infusion set at least every 3 days.
- The insulin cartridge and tubing will be replaced as needed, but no less often than every 3 days.
- A new Dexcom CGM sensor will be placed every 10 days if no replacement was required before this time. The iLet will generate an alarm when replacement is required.
- Participants will be asked to charge their iLet routinely (preferably at least once daily, such as when they are bathing) and whenever they notice the battery level is low. The iLet will alarm at low battery thresholds.
- Participants will not tamper with or alter the iLet device in any way.
- The iLet is water resistant but participants will be instructed to remove it for showering and swimming and to keep it dry during exercise.
- Participants will be trained to take appropriate precautions when they are disconnected from the iLet, including frequent BG checks using the study Contour Next One glucometer if they are not monitoring CGM glucose by another method (e.g. their phone) and to have carbohydrate readily available. They are urged to limit the amount of time they are disconnected from the iLet to ensure optimal glucose control.
- If a participant develops an illness during the study, they can seek medical care as usual. If the participant is unable to eat for a period exceeding one day, they must notify study staff so that the medical staff can assess the safety of continuing to use the iLet. Use of the iLet may be temporarily discontinued if study staff believe this is warranted.
- If a participant discontinues use of the iLet either due to investigator judgment that it is not safe for the participant to continue to use the iLet or the participant's choice, the participant will return to their pre-study insulin delivery and glucose monitoring method and will be instructed to contact their usual diabetes care provider in case any questions or concerns arise about their usual diabetes care following cessation of study activities.

5.7.3 *Alarm Settings and Response to Hypoglycemia and Hyperglycemia*

All alarm settings will be the same during both BP arms. The blinded CGM will not have any alarms. Participants using their personal CGM as part of their usual care will be instructed to follow the alarm settings prescribed by their diabetes care provider.

- Alarms will sound and a visual alert will appear on the screen of iLet when the CGM glucose is \leq 55 mg/dl. There is an optional additional hypoglycemia alarm at 75 mg/dl. Study staff will recommend participants use this alarm as well.
 - Participants will be trained to test their BG with the study glucometer in response to such

an alarm and take any necessary measures to treat hypoglycemia as described in section 5.7.2.

- An optional alarm will sound, and a visual alert will appear on the iLet if CGM glucose is > 300 mg/dl for 90 minutes. Study staff will recommend participants use this alarm.
 - Participants will be trained to test their BG with the study glucometer in response to such an alarm and take any necessary measures to treat hypoglycemia as described in section 5.7.2.

5.7.4 *Supervision by study staff*

A study provider (MD or NP) will be on call at all times during the course of the study to answer questions and address any issues that arise. The Beta Bionics technical support center will be readily available by phone consultation at all times to assist with any needed troubleshooting.

A study provider (MD or NP) will respond to calls regarding ketosis concerning for DKA or severe hypoglycemia requiring assistance from another person. In such circumstances, the study MD or NP will speak directly to the participant (or to the person assisting them). The Site PI must be informed within one hour if they are not already aware of the event. If the site PI will not be available, then the site PI will designate another investigator for the period during which they will not be available so that it is clear who has this responsibility.

If based on their experience and judgment study staff believes that the participant needs emergency care, they should recommend to the participant that the participant go to an emergency department. Study staff should determine which emergency department the participant will be taken to and follow up within 15 minutes of the expected arrival time to make sure the participant arrived. If the study staff calls 911, they should remain on the telephone with the participant (or the person assisting the participant) until the ambulance arrives and speak to the Emergency Medical Technicians to provide history and determine where the participant will be taken.

Whenever a participant is sent to the emergency department, study staff must confirm that the participant has arrived at ED within an hour, and a study staff member should attempt to speak with a member of the medical staff (e.g., physician, PA, NP, nurse) at the emergency department to confirm arrival and provide information about the reason for referral to the ED.

If there is serious concern for the well-being of the participant and the participant cannot be reached within 15 minutes in the case of glucose < 55 mg/dL or 90 minutes in the case of glucose > 300 mg/dL, then study staff should attempt to reach close contacts. If no contacts are available or their contacts do not succeed in reaching them, then 911 should be called immediately and a well-being check should be requested. Study staff must follow up on and document the results of the well-being check.

6 Biostatistical Analysis

